## **Protocol Summary**

Title of study	A post-marketing surveillance study for Repatha Inj. (evolocumab) in Korea (Protocol No.: 20160156)			
Protocol version	1.1			
Date of final protocol version				
Study (PAS) Enrollment No. following				
EU approval	NA			
Active ingredient	Evolocumab, AMG 145			
Brand name	Repatha Inj.			
Reference drug	NA			
Procedure No.	NA			
Sponsor	Amgen Korea			
Associated PASS	None			
Objective of study	To assess the safety and efficacy of Repatha Inj. in post-marketing routine clinical settings			
Country of study	Korea			
Author				

### 2. List of abbreviations

ADE	Adverse device effect
ADR	Adverse drug reaction
AE	Adverse event
CABG	Coronary artery bypass graft
CKD	Chronic kidney disease
CRF	Case report form
CVD	Cardio vascular disease
eGFR	estimated Glomerular filtration rate
FH	Familial hypercholesterolemia
FSE	First subject enrolled
HoFH	Homozygous familial hypercholesterolemia
ICJME	International committee of medical journal editors
IRB	Institutional review board
LDL-C	Low-density lipoprotein cholesterol
LDL-R	Low-density lipoprotein receptor
LSLV	Last subject last visit
MedDRA	Medical dictionary for regulatory activities
MFDS	Ministry of food and drug safety
PAD	Peripheral arterial disease
PCI	Percutaneous coronary intervention
PCSK9	Proprotein convertase subtilisin/kexin type 9
PT	Preferred term
RMP	Risk management plan
SAE	Serious adverse event
SADR	Serious adverse drug reaction
SD	Standard deviation
SOC	System organ class
SOP	Standard operating procedure
тс	Total cholesterol
TG	Triglyceride
WHO ATC code	World health organization anatomical therapeutic chemical code

### 4. Synopsis

### • Title of study

A post-marketing surveillance study for Repatha Inj. (evolocumab)

### • Study background and rationale

According to Rule on Safety of Drugs etc. in Korea (enforced 01 Jul 2015), an applicant for product approval is responsible for submitting risk management plan for new drugs, orphan drugs, drugs acknowledged by the Minister of Food and Drug Safety for required submission of risk management plan, or drugs for re-examination for marketing authorization application.

In addition, according to Article 32 of Pharmaceutical Affairs Act, Article 22 of Rule on Safety of Drugs etc., and Regulation on Re-examination of New Drugs etc. (Ministry of Food and Drug Safety [MFDS] Notification No. 2016-97), it is required to conduct a study on the safety and efficacy of the drug for 6 years from the date of drug approval in the target number of patients calculated based on the prevalence of the applicable indication.

Amgen has submitted an application for marketing authorization of Repatha Inj. as combination therapy with other cholesterol lowering agents in adults and adolescents aged 12 or older with Homozygous Familial Hypercholesterolemia (HoFH).

### • Study questions and objectives

### 1) Primary objective

The primary objective of this study is to assess the incidence rate of adverse events (AEs) (including device related AEs) and adverse drug reactions (ADRs) for up to 12 weeks in patients who are prescribed Repatha Inj. according to the approved therapeutic indications, dosage, and administration in post-marketing settings (see Section 11 for definitions of terms). In addition, profiles of AEs and ADRs will be analysed.

### 2) Secondary objective

The secondary objective of this study is to assess the efficacy of Repatha Inj. and to identify the characteristics of treated patients (e.g., demographics and medical history).

### • Study design/type

This is a single arm, prospective, observational study. To meet the criteria and form recommended by the MFDS, the safety and efficacy of Repatha Inj. will be assessed in post-marketing settings for 6 years after drug approval in the target number of patients calculated based on the prevalence of the indication.

### Subjects/data collection

### 1) Subjects

Patients who meet the inclusion/exclusion criteria for this study will be enrolled for 6 years after approval of Repatha Inj. in Korea.

### 2) Data collection

The study drug, Repatha Inj., is available in the market for prescription by the investigator for therapeutic purposes.

Case report forms (CRFs) will be designed to collect the primary endpoint, secondary endpoints, and other study item related information from baseline and throughout the follow-up period. The investigator (the treating physician participating in this study) should prepare the CRFs.

### • Summary of subject eligibility criteria

- 1) Inclusion criteria
- HoFH patient treated with Repatha Inj. according to the approved therapeutic indications, dosage, and administration in post-marketing settings
- · Patient who voluntarily provided written informed consent

### 2) Exclusion criteria

- Patient who did not provide written informed consent
- There are no other exclusion criteria.

### • Follow-up

Each patient will be followed up from the first Repatha Inj. dose to Week 12 of treatment, death, or lost to follow-up (e.g., patient transfer to another hospital), whichever is earlier.

### • Endpoints

### 1) Primary endpoint

The primary endpoint is the incidence rate of AEs/ADRs observed or reported to the investigator during the follow-up period. All AEs will be classified using Medical Dictionary for Regulatory Activities (MedDRA).

If sufficient data is collected, seriousness and causal relationship to drug or device can be also analyzed.

- 2) Secondary endpoints
- Efficacy measurement; change in low-density lipoprotein (LDL)-cholesterol (LDL-C) measured as part of routine clinical practice from baseline to the end of follow-up
- Patient characteristics (for details, see Section Error! Reference source not found.)
  - Demographic information and medical history
  - o Diagnosis of hypercholesterolemia
  - Concomitant medication prior to study participation
  - o Other concomitant medication

### • Number of subjects

Amgen plans to follow up 10 patients who meet the inclusion/exclusion criteria for this study for 6 years after approval of Repatha Inj. in Korea.

Based on the low diagnosis rate and prevalence of HeFH ( $1/160,000 \sim 1,000,000$  individuals), number of subjects estimated is approximately 10 subjects.

### • Data analysis

Categorical variables will be summarized with frequency and percentage, and continuous variables will be summarized with mean, standard deviation (SD), standard error (SE), median, Q1, Q3,

minimum, and maximum. Subject disposition, demographic information, and baseline characteristics will be summarized in the safety set.

For safety analysis, number of subjects, number of events, and incidence rate will be presented in the safety set for AEs (including device related AEs), ADRs, and serious AEs (SAEs). 95% confidence interval will not be calculated because it is not meaningful for the planned sample size of 10 subjects. For efficacy analysis, change (%) in LDL-C at Week 12 from baseline will be analysed in the efficacy set.

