## 7.3. Statistical inference (assumption or hypothesis)

There is no formal hypothesis to be tested in this study. Instead, the proposed post-marketing surveillance study will provide descriptive data for the safety and efficacy of Repatha Inj. in routine clinical settings after marketing approval with HoFH patients in Korea.

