### 9.5. Number of subjects

Amgen plans to recruit in a consecutive manner 10 patients who meet the inclusion/exclusion criteria for this study for 6 years after approval of Repatha Inj. in Korea.

Based on the low diagnosis rate and prevalence of HeFH ( $1/160,000 \sim 1,000,000$  individuals), number of subjects estimated is approximately 10 subjects.

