## 9.7.2.2. General considerations

All analyses will be performed with SAS 9.4 or higher version. In principle, two-sided statistical tests will be performed at a significance level of 5%, and up to two digits after the decimal point will be presented in summary statistics.

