### 9.9. Limitation in study methodology

Because of its prospective, observational nature, this study is more greatly affected by bias than interventional clinical trials are. Below is the summary of methods to reduce common limitations and errors identified in this type of study.

· Missing and incomplete data including lost to follow-up

The investigator should be given clear guidelines for CRF completion for this study to ensure that he/she makes every effort to collect complete data.

- Selection bias, information bias, and confounding factors
  - Most patients treated with Repatha Inj. in post-marketing settings in Korea are expected to enroll in this study. This will be helpful in restricting selection bias.

- Amgen will prepare a list of potential institutions/investigators who can prescribe Repatha Inj. to HoFH patients in post-marketing settings. Based on this data, Amgen will visit each of the potential institutions prior to study initiation to evaluate feasibility of the institutions and to confirm the potential investigators' interest in and willingness for study participation. Study institutions will be selected based on the results of these pre-study site visits.
- Amgen will ask all known physicians who prescribe Repatha Inj. If a physician who was asked to conduct the study for Repatha Inj does not want to participate in the study, Amgen will record the reason in writing.
- Before the study begins, initiation visits will be carried out to complete site trainings for the protocol and other study specific procedures. At the initiation visits, the rareness of the disease will be explained, and the investigators will be asked to make every effort to enroll all eligible HoFH patients in a consecutive manner.
- There is a possibility that patients enrolled in this study (e.g., patients who will be treated with Repatha Inj.) are likely to have a severer form of the disease than those HoFH patients who are not prescribed Repatha Inj. (patients not included in the study). This confounding by indication bias would limit the generalization of safety and efficacy results.
- Analysis results should be interpreted with sufficient understanding of these study limitations. Of those, the most significant limitation is due to the very small number of patients to be enrolled. The very limited number of patients would limit the power of inference of this study because of lack of accuracy in estimation.

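### The synopsis rules out a 95% confidence interval for the primary safety incidence because n is 10; that reason is unsound and leaves the primary result with no planned measure of uncertainty

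*Protocol*

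**What the plan says.** The study is single-arm and descriptive. On size, the Synopsis says that the "number of subjects estimated is approximately 10 subjects", and Section 9.5 repeats the target: "Amgen plans to recruit in a consecutive manner 10 patients who meet the inclusion/exclusion criteria". The figure is attributed to prevalence and a low diagnosis rate; no precision target is given.

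On the primary endpoint, the Synopsis says: "The primary endpoint is the incidence rate of AEs/ADRs observed or reported to the investigator during the follow-up period". For its analysis, the Synopsis (Data analysis) says that "number of subjects, number of events, and incidence rate will be presented in the safety set for AEs", and for ADRs and serious AEs (SAEs) as well. It then adds that a "95% confidence interval will not be calculated because it is not meaningful for the planned sample size of 10 subjects". Section 9.7.2.4.3 lists the same three quantities; it neither repeats the exclusion nor supplies an interval.

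Three other statements bear on this:

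- Section 7.3: "There is no formal hypothesis to be tested in this study".
- Section 9.7.2.2 provides, in principle, that "two-sided statistical tests will be performed at a significance level of 5" percent.
- Section 9.9 names the small number of patients as the most important limitation: "The very limited number of patients would limit the power of inference of this study because of lack of accuracy in estimation".

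The Synopsis also plans a standard error for continuous variables at the same sample size.

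**The concern.** This is a stated decision with a stated reason, not a detail left for the statistical analysis plan. A later plan could supply the interval only by contradicting the protocol.

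The reason confuses a wide interval with an uninformative one. With no hypothesis to test, estimation is the whole purpose of the study. If 10 patients are enough to print an incidence, they are enough to print its uncertainty. The document is also uneven: it plans a standard error for continuous variables, keeps significance tests in principle, and warns in words about imprecision, yet removes the one statistic that would put a number on that imprecision for the primary endpoint.

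What is at stake is how the safety tables are read. Individual ADRs, SAEs and device-related AEs will often have a count of zero among 10 patients. A zero incidence with nothing beside it looks more reassuring than the data allow. The same format would presumably be used in the periodic reports of Section 9.7.1.1, where early reports may cover fewer than 10 patients.

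**Working it through.** **Inputs**

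- n = 10 (Synopsis, Number of subjects; Section 9.5). This is a feasibility count. The protocol gives no population size, diagnosis rate or formula, so it can be neither reproduced nor refuted here.
- Denominator: the safety set (Section 9.7.2.1). It equals 10 only if every enrolled patient has at least one dose and one safety follow-up.
- Assumption: the incidence is the number of patients with at least one event divided by the safety set, so the binomial model applies. It does not apply to the number of events, since one patient can have several.

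**Zero events.** The two-sided exact 95% upper limit solves (1 − p)^n = 0.025, so p = 1 − 0.025^(1/n). For n = 10: 1 − 0.025^(0.1) = 0.3085, or 30.8%. Check: at p = 0.3085 the probability of 0 events in 10 is 0.025.

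**One or more events.** The Clopper-Pearson limits are beta quantiles: lower = B(0.025; x, n − x + 1), upper = B(0.975; x + 1, n − x).

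| Patients with event | Exact two-sided 95% interval |
|---|---|
| 0/10 | 0% to 30.8% |
| 1/10 | 0.3% to 44.5% |
| 2/10 | 2.5% to 55.6% |
| 3/10 | 6.7% to 65.2% |
| 5/10 | 18.7% to 81.3% |

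**Does the method matter?** For 0/10 the upper limit is 25.9% (one-sided exact 95%), 27.8% (Wilson) or 30.0% (rule of three). All lie between about 26% and 31%.

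**Does the denominator matter?** If fewer patients qualify (assumed counts), 0/9 gives 33.6% and 0/8 gives 36.9%. For an early periodic report, also with assumed counts, 0/5 gives 1 − 0.025^(1/5) = 52% and 0/3 gives 1 − 0.025^(1/3) = 71%.

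**How likely is a zero count?** The probability of no events among 10 patients is (1 − p)^10. It is 0.599 for a true 12-week incidence of 5%, 0.349 for 10% and 0.107 for 20%. This follows from the sample size and no interval cures it, but it shows that zero counts will be common and need an upper limit beside them.

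**Sections 7.3 and 9.7.2.2 side by side.** The first says there is no formal hypothesis. The second sets a sidedness and a significance level for tests, in principle. Nothing in the analysis sections names a test. The two statements need reconciling whatever is decided about the interval.

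**The case against.** The best defence is that nothing is hidden. The plan reports the number of patients and the number of events with each incidence, and the disposition table in Section 9.7.2.4.1 gives the size of the safety set. A reader therefore sees 0 of 10, and x and n fix the exact limit. Section 9.9 already warns that estimation is imprecise. No decision rule, error rate, sample size or data collection depends on the interval, and it can be computed later from the planned tables. The protocol also calls the interval not meaningful rather than invalid, which is a judgement.

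Most of this stands, and it limits the point. A reader might infer that the incidence would appear as a bare percentage, or that a regulator could not work out what risk is excluded. The documents do not support that, because the counts are there. A reader might also expect a zero to be printed to two decimals, but Section 9.7.2.2 sets up to two decimals as a ceiling. Nor is 31% a general bound on the primary result. It needs zero events in a category and a full safety set of 10. For any AE, zero is only one possible outcome, and the endpoint text makes analysis of seriousness conditional on sufficient data, although the Data analysis paragraph does list SAEs.

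The defence does not rescue the reason given. A judgement that an interval such as 0.3% to 44.5% has no meaning is hard to square with printing the 10% point estimate, or with planning a standard error for other variables at the same n. A warning in words does not replace a number.

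**Conclusion.** The point holds as a reporting weakness that should be corrected, not as a flaw that invalidates the study. The protocol excludes the interval for its primary endpoint on an unsound ground and plans no other measure of uncertainty for it. With a safety set of 10, zero events are compatible with an incidence of up to 30.8%, and one event with 0.3% to 44.5%. These figures assume a subject-level proportion, independent patients, a full safety set of 10 and the two-sided exact method; with fewer patients the limits are wider.

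A reader might go further and treat the omission as something that must be fixed before the study can proceed. The documents do not support that: the study is descriptive, the counts are reported, and imprecision is acknowledged. Nor does the point extend with the same force to LDL-C. The no-interval sentence follows the safety outputs and precedes the efficacy sentence, so its reach to LDL-C is unclear, and an SD and standard error are already planned for continuous variables.

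The conflict between Sections 7.3 and 9.7.2.2 is real but separate, and is softened by the qualifier that tests are done in principle.

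**What to change.** 1. In the Synopsis (Data analysis), delete the sentence that excludes the interval.
2. In the Synopsis and in Section 9.7.2.4.3, state instead, for example:

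> The proportion of patients with at least one AE, ADR, SAE or device-related AE will be shown as x/n with an exact (Clopper-Pearson) two-sided 95% confidence interval. Where x = 0, the upper limit will be given. The intervals are descriptive. Numbers of events will be shown without a binomial interval.

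3. In Section 9.7.2.2, replace the provision for two-sided 5% tests with a statement that no hypothesis tests are done, in line with Section 7.3.
4. Optional: a t-based 95% interval for the mean LDL-C change.

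The cost is a few sentences and one extra table column. No additional patients, visits or data are needed.

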## 5. Amendments and updates

Not applicable

### 6. Milestone

- Expected date of protocol approval: (approval of the draft by Amgen); The final approval is expected to occur when drug approval is obtained from the MFDS.
- Expected date of study initiation (first subject enrolled): (The actual date of market release is subject to change according to the market release schedules in Korea.)
- Planned study institutions: all institutions that agree to participate in the study and treat HoFH patients with Repatha Inj. (approximately 30 institutions)
- Expected subjects/patients: All HoFH patients who agree to participate in this study and are prescribed Repatha Inj. (10 patients)
- Planned duration of enrollment/data collection: Patients will be enrolled for 6 years after approval of Repatha Inj.; Data will be collected until the last subject completes his/her last visit.
- Duration of study (e.g., duration from the first subject enrolment to the last subject's last visit); 6 years and 3 months
- Duration of observation for individual subjects: 12 weeks
- Expected date of final report: within 3 months after the end of re-examination period

## 7. Study rationale and background

## 7.1. Disease and therapeutic indication

HoFH is a genetic disorder primarily caused by homozygous mutations of the LDL receptor (LDLR) gene. HoFH is most commonly caused by mutations of both alleles of LDLR, resulting in decreased uptake and removal of LDL. HoFH patients with LDLR gene mutations may be either true homozygotes (having the same mutation in both alleles of LDLR) or compound heterozygotes (having different mutations in each allele of LDLR). Patients with HoFH may have severe hypercholesterolemia associated with LDL-C accumulation in plasma, tendon, and skin, and develop progressive atherosclerosis and, particularly coronary heart disease, typically within 20 years from birth. Worldwide, the prevalence of HoFH is estimated to be 1/160,000 to 1,000,000 individuals.

## 7.2. Study rationale

According to Rule on Safety of Drugs etc. in Korea (enforced 01 Jul 2015), an applicant for product approval is responsible for submitting risk management plan for new drugs, orphan drugs, drugs acknowledged by the Minister of Food and Drug Safety for required submission of risk management plan, or drugs for re-examination for marketing authorization application.

In addition, according to Article 32 of Pharmaceutical Affairs Act, Article 22 of Rule on Safety of Drugs etc., and Regulation on Re-examination of New Drugs etc. (MFDS Notification No. 2016-97), it is required to conduct a study on the safety and efficacy of the drug for 6 years from the date of drug approval in the target number of patients calculated based on the prevalence of the applicable indication.

## 7.3. Statistical inference (assumption or hypothesis)

There is no formal hypothesis to be tested in this study. Instead, the proposed post-marketing surveillance study will provide descriptive data for the safety and efficacy of Repatha Inj. in routine clinical settings after marketing approval with HoFH patients in Korea.

## 7.4. Product background

Repatha Inj. (evolocumab) is a fully human monoclonal IgG2 antibody designed to inhibit Proprotein Convertase Subtilisin/Kexin type 9 (PCSK9).

Upon parenteral administration, Repatha Inj. (evolocumab) inhibits the binding of circulating PCSK9 to LDLR on liver cells, thereby interfering with PCSK9-mediated LDLR degradation. This increases LDLR levels in liver, resulting in a decrease in associated blood LDL-C levels.

## 8. Study questions and objectives

## 8.1. Primary objective

The primary objective of this study is to assess the incidence rate of AEs (including device related AEs) and ADRs for up to 12 weeks in patients who are prescribed Repatha Inj. in post-marketing settings (see Section 11 for definitions of terms). In addition, profiles of AEs and ADRs will be analysed.

### 8.2. Secondary objective

The secondary objective of this study is to assess the efficacy of Repatha Inj. and to identify the characteristics of treated patients (e.g., demographics and medical history).

## 8.3. Exploratory objective

Not applicable

### 9. Study methodology

This is a single arm, prospective, observational study. To meet the criteria and form recommended by the MFDS, the safety and efficacy of Repatha Inj. will be assessed in post-marketing settings after drug approval in patients treated with this drug according to the approved therapeutic indications, dosage, and administration.

## 9.1. Study design

This is a single arm, prospective, multicentre, observational study in HoFH patients treated with Repatha Inj. in Korea. According to regulatory guidelines, duration of enrolment is 6 years after drug approval in Korea.

Each patient will be followed up from the first Repatha Inj. dose to Week 12 of treatment, death, or lost to follow-up (e.g., patient transfer to another hospital), whichever is earlier.

